### **Efficacy Assessments**

Right Heart Catheterization (RHC): RHC is performed routinely as a clinical standard of care procedure for diagnostic purposes in this population. RHC will be performed at Screening and at the end of the treatment (Visit 6 – Week 12).

Briefly, RHC will be performed with a balloon tipped, flow-directed, pulmonary artery catheter (e.g. 7F Swan Ganz catheter) inserted through a sheath in the internal jugular vein under continuous

ECG monitoring. An alternate vein may be used at the physician's discretion. All measurements will be recorded with the subject in a supine position, at rest, breathing room air or with supplementary oxygen to obtain peripheral saturations above 90%. Hemodynamic recording of right atrial, right ventricular, pulmonary artery pressures, pulmonary artery wedge pressure and cardiac output will be made. Parameters for analysis will include: Mean RAP, RVSP, RVDP, PASP, PADP, Mean PAP, Mean PAWP, Thermodilution Cardiac Output, PVR, Cardiac Index, and Pulmonary Vascular Compliance. Mixed venous oxygen saturation (SvO2) will be determined from a sample drawn from the Swan-Ganz catheter. Other parameters may be obtained as data permit.

**Echocardiogram:** Noninvasive transthoracic echocardiograms will be completed to assess RV function by measures such as tricuspid annular plane systolic excursion (TAPSE) as well as tissue Doppler of the lateral tricuspid valve anulus (S').

**Six Minute Walk Distance Test and Borg Dyspnea Scale:** The 6MWD test will be performed according to a protocol-specific modification of the American Thoracic Society guidelines. The 6MWD test measures the distance an individual is able to walk over a total of six minutes on a hard, flat surface. The Borg Scale is a method of rating perceived exertion during exercise. It should be performed immediately after the 6MWD test.

**Physical Activity:** Continuous physical activity monitoring will be conducted using a noninvasive accelerometer (Actigraph, Pensacola, FL). All subjects will be instructed to use a noninvasive accelerometer at home during waking hours to quantify physical activities for 8 days to achieve a full 7 wear days, and to take it off only when showering. Measurements will include sleep and wake activity over the entire 24-hour period each day it is worn. The device must be worn for a minimum of 7 consecutive days at home prior to: (1) receiving the first dose of study medication (Visit 3 - Week 0) in order to collect baseline activity, and (2) prior to conducting end of study drug treatment assessments at Visit 6 (Week 12). The study staff will remove the accelerometer when the subject returns for Visit 3 and Visit 6. The study staff will download the data, visually screen the raw accelerometer file for spurious data, perform a battery check, and allocate the unit for redeployment.

**N-Terminal Pro-B-Type Natriuretic Peptide (NT-proBNP):** Blood samples for determination of NT-proBNP serum concentrations will be collected at Screening and at 4-week intervals throughout the study.

**WHO Functional Class:** The World Health Organization (WHO) Classification of Functional Status of Patients with PH will be used to classify disease severity in PAH. It places patients in one of four categories based on how much they are limited during physical activity.

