## **2.4 STUDY ENDPOINTS**

Primary Endpoint:

The primary endpoint measures the incidences of treatment-emergent adverse events.

Secondary Endpoints:

The primary efficacy endpoint measures the change from baseline in Pulmonary Vascular Resistance (PVR) assessed by Right Heart Catheterization at 12 weeks.

Other secondary endpoints measure:

- Change from baseline in hemodynamic parameters including Cardiac Output (CO), Cardiac index (CI), mean Pulmonary Artery Pressure (mPAP), Pulmonary Artery Wedge Pressure (PAWP), Mean Right Atrial Pressure (mRAP), and compliance (SV/ (sPAP-dPAP) at 12 weeks
- Change from baseline in RV function including tricuspid annular plane systolic excursion (TAPSE) and tissue Doppler of the lateral tricuspid valve anulus (S') as assessed by echocardiograms at 12 weeks
- Change from baseline in functional exercise capacity by assessing 6 minute walk distance test with Modified Borg Dyspnea Scale at 12 weeks
- Change from baseline in the levels of serum NT-proBNP at 12 weeks
- Change from baseline in WHO Functional Class at 12 weeks
- Change from baseline in patient reported outcomes measured by PAH-SYMPACT® questionnaire at 12 weeks
- Change from baseline in daily physical activity assessed by personalized activity monitor at 12 weeks
- Pharmacokinetic endpoint: CXA-10 parent and metabolites

Exploratory Endpoints:

- Change in insulin sensitivity by intravenous glucose tolerance test at 12 weeks
- Pharmacodynamic endpoint: change from baseline in serum biomarkers, leptin, inflammatory cytokines (IL-17, IL-6, TNF $\alpha$ , MCP-1) and hsCRP at 12 weeks
- Pharmacokinetic - Pharmacodynamic relationship of CXA-10 on relevant efficacy, safety and biomarkers endpoints, if the data allow
- Epidemiological relationships of oral and gut microbiome and PAH

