## 2.5 STATISTICAL ANALYSIS

### 2.5.1 Sample Size Determination

We plan to enroll 30 subjects with PAH, allowing for a conservative drop-out rate of 10%, in this open label trial of oral CXA-10. We expect to see decrease in the PVR after 12 weeks of therapy. The intention to treat (ITT) population will consist of all subjects who have received at least one dose of study medication. To estimate our effect size for power calculations, we use data from the SUPER-1 sildenafil PAH trial (a randomized placebo control trial evaluating the effects of 20 mg, 40 mg or 80 mg TID of sildenafil in subjects with PH). Using the hemodynamic data from the 80 mg arm of the SUPER-1 trial and making a conservative assumption that our therapy will only have an effect that is 70% of sildenafil (decrease in PVR of 2.3 woods units with SD of 4.1), the sample size required for 80% power and P = 0.05 is 27 subjects (Table 2). We anticipate more than sufficient power to detect vasodilatory effects of NO2-OA administration (decreased PVR) after 3 months of therapy. Based on our extensive phase 1 data with CXA-10 formulations, we

anticipate the drug will cause no systemic blood pressure changes and no increases in methemoglobin levels.

**Table 2 Required sample size for different effect,  
Power =0.8 ,  $\alpha=0.05$ , two sided test**

% of Sildenafil	Mean (SD) PVR change, Woods unit	N
90	3.0 (4.9)	23
80	2.6 (4.2)	23
70	2.3 (4.1)	27

With safety as the primary outcome measure, we use Fleming's single stage phase II design with the following assumptions:  $\alpha = 0.05$ , Power= 0.80, lower proportion for rejection 70% (with no SAEs), higher proportion of acceptance 90% (with no SAEs) with maximum recruited patients of 27 patients resulting in a minimum number of success (with no SAEs to indicate that the treatment is safe) is 24. Thirty patients will be enrolled to compensate for up to 10% lost-to follow-up.

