## 2.5.2 Statistical Analysis

Change of each outcome from baseline will be presented by median (IQR). Primary analysis will be performed by paired t-test comparing continuous outcome in 12-weeks vs. baseline. All data will be tested for normality, and non-normal data will be tested by Wilcoxon signed rank test. We will also use mixed effect models with restricted maximum likelihood estimation to test the change of outcome during the 12 weeks of intervention.

Demographics and baseline characteristics will be listed and summarized descriptively. Safety will be evaluated via the incidence of AE's, changes in clinical labs, and vital signs. AEs will be coded by system organ class and preferred term according to the most recent edition CTCAE. AEs will be summarized by frequency, severity, and relationship to study medication. Clinical labs will be compared to normal ranges and flagged if found to be of clinical concern. Results will be presented as observed changes and depicting changes from baseline to defined study timepoints.

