## **3.2 INCLUSION CRITERIA**

The following criteria will be required on ALL subjects:

- Male or female between 18-80 years of age inclusive at Screening
- Weight  $\geq$  40 kg or 88 lbs
- Have a WHO Classification of Functional Status Class II or III
- Must meet all of the following hemodynamic criteria by means of a right heart catheterization: mPAP of  $\geq$ 25 mmHg, PVR  $\geq$  3 wood units, PAWP of  $\leq$ 15 mmHg. A clinical RHC done within 2 months is acceptable to determine eligibility
- Meet all of the following pulmonary function test parameters, completed no more than 12 months before Screening or at screening: forced expiratory volume in one second (FEV1)  $\geq$  60% of predicted normal and forced vital capacity (FVC)  $\geq$  60%
- A 6 MWD test of  $\geq$  100 m and  $\leq$  600 m at Screening
- Participants enrolled in an exercise program for pulmonary rehabilitation must be in a stable program 1 month prior to Screening and must agree to maintain their current level of rehabilitation throughout the study. If subjects are not enrolled in an exercise training program for pulmonary rehabilitation they cannot enroll during the Screening/Baseline Period or throughout the study
- If receiving 3-hydroxy-3-methyl-glutaryl-coenzyme A (HMG-CoA) reductase inhibitors (i.e., statins) subjects must not have changed their dose  $<$ 4 weeks prior to Screening
- If receiving simvastatin-containing products: simvastatin (Zocor), Vytorin, or any other combination therapy containing simvastatin, the subject's simvastatin dose should not exceed 20 mg/day  
Note: Subjects using a simvastatin product at dose  $>$  20 mg/day may be rescreened if their dose has been adjusted to  $\leq$  20 mg/day, at least 4 weeks prior to Screening with no dose or regimen changes within 4 weeks prior to Baseline
- Subjects must be receiving one or more of the following previously approved PAH therapies: phosphodiesterase type 5 inhibitors (PDE5), endothelin receptor antagonist (ERA), soluble guanylate cyclase (sGC) stimulator, prostanooids, prostacyclin receptor agonists and must be on stable doses ( $\geq$  3 months) with no dose adjustment within 1 month of Screening
- Ability to provide written informed consent

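### WHO Functional Class is a four-category endpoint, but its change is to be presented as median (IQR), which prints the same 0 (0, 0) for quite different results

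*Combined protocol and SAP*

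**What the plan says.** Section 2.2.3 (Efficacy Assessments) defines the scale as Classes I to IV: "It places patients in one of four categories based on how much they are limited during physical activity". Section 2.4 lists "Change from baseline in WHO Functional Class at 12 weeks" among the secondary endpoints. Section 3.2 restricts entry: "Have a WHO Classification of Functional Status Class II or III".

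Section 2.5.2 has a single rule for presenting change: "Change of each outcome from baseline will be presented by median (IQR"). For testing it says "Primary analysis will be performed by paired t-test comparing continuous outcome in 12-weeks vs. baseline", and adds that "non-normal data will be tested by Wilcoxon signed rank test". It also plans a model: "We will also use mixed effect models with restricted maximum likelihood estimation to test the change of outcome during the 12 weeks of intervention". Section 2.5.5 uses the mixed model to deal with missing data for endpoints measured at more than baseline and Week 12. WHO class is one of these, since Appendix A also records it at Weeks 4 and 8.

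Section 2.5 has no shift table for WHO class, no count or percent improved or worsened, and no categorical or ordinal method. The frequency tables in Section 2.5.2 are for adverse events, and its descriptive summaries are for demographics and baseline characteristics.

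**The concern.** A subject who enters in Class II or III can move by at most two classes in either direction, so the change takes only the values -2, -1, 0, 1 and 2. If many subjects stay in their class, the zeros occupy the middle of the ordered values, and the median and both quartiles can all be zero whatever happens at the two ends.

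In a single-arm study of this size, the useful facts about functional class are how many subjects moved up and how many moved down. Worsening also bears on tolerability, which is part of the main objective. The planned summary can leave both numbers out.

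**Working it through.** **Inputs.** n = 27 completers (Section 2.5.1). Entry class II or III (Section 3.2). Two-sided alpha 0.05, which Table 2 states for PVR and which is assumed here for WHO class. One-class shifts, also an assumption, because the documents give no expected rate of class change. Improvement is coded -1, no change 0, worsening +1.

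**The plan's own figure.** For PVR with mean change 2.3 and SD 4.1, the noncentral t power of a paired t-test at n = 27 is 0.801, so 27 reproduces. Allowing 10% dropout, 27/(1 - 0.10) = 30, which also reproduces.

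**When the summary prints 0 (0, 0).** Order the 27 changes.

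- The median is the 14th value. It is 0 unless at least 14 subjects move the same way.
- The lower quartile lies between the 7th and 8th values (position 7 or 7.5 under two common definitions). With 6 or fewer improvers the 7th value is at least 0.
- By symmetry, the upper quartile is 0 with 6 or fewer worseners, if improvers are also 6 or fewer.

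So all 7 × 7 = 49 combinations of 0 to 6 improvers and 0 to 6 worseners print 0 (0, 0).

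| Improved | Unchanged | Worsened | Printed summary | Exact signed-rank p |
|---|---|---|---|---|
| 0 | 27 | 0 | 0 (0, 0) | none (no movers) |
| 3 | 21 | 3 | 0 (0, 0) | 1.00 |
| 6 | 21 | 0 | 0 (0, 0) | 0.031 |
| 0 | 21 | 6 | 0 (0, 0) | 0.031 |
| 8 | 19 | 0 | 0 (-1, 0) | below 0.031 |
| 13 | 14 | 0 | 0 (-1, 0) | below 0.031 |

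With 8 to 13 improvers and none worsening (8/27 = 30% to 13/27 = 48%), the 7th and 8th values are -1 and the 14th is 0, so the summary is 0 (-1, 0) throughout. At 14 improvers the median becomes -1.

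**Tests on the same data.** With m subjects moving, all in one direction, the exact two-sided signed-rank p is 2 × (1/2)^m: 0.125 for m = 4, 0.0625 for m = 5 and 0.031 for m = 6. For the paired t-test at m = 6, the mean is -6/27 = -0.222, the SD is √(6 × 21/(27 × 26)) = 0.424, the SE is 0.424/√27 = 0.0815, and t = -2.73 on 26 df, p = 0.011. At m = 4 the paired t-test already gives p = 0.043.

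**How often significance and 0 (0, 0) coincide.** Of all splits of 27 subjects into improved, unchanged and worsened, 194 are significant at 0.05 by the exact test. Only two of these print 0 (0, 0): 6-0 and its mirror 0-6. At 7 movers a quartile leaves 0.

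**Sensitivity.** One uncommon quantile definition (interpolated inverted CDF) gives a lower quartile of -0.25 for 6 improvers at n = 27. For n = 28 to 30, the 6-0 and 0-6 patterns print 0 (0, 0) under every definition tried. At n = 24 or 25 the 6-mover result depends on the definition.

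**The case against.** The strongest reply is that little is lost. Three parts of it stand.

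First, a reader might infer that the summary can never separate improvement from worsening. It can: 8 improvers print 0 (-1, 0) and 8 worseners print 0 (0, 1). The IQR shows direction once about a quarter or more of subjects move one way. What is lost is resolution, not all information.

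Second, a reader might infer that 0 (0, 0) beside a small p-value is a contradiction, or that the pairing would be common. Neither follows. The signed-rank test drops the zeros and the median keeps them, and by the exact test the pairing is confined to 6-0 and its mirror.

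Third, median (IQR) is not the only planned output. WHO class is measured repeatedly, so the mixed model of Sections 2.5.2 and 2.5.5 could give a signed mean change. A mean change in class, however, does not say how many subjects improved and how many worsened.

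A reader might also infer that the test is wrong and needs replacing. The documents do not support that. Section 2.5.2 confines the t-test to continuous outcomes, and when all changes are one class the exact signed-rank test is the sign test.

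It can also be said that nothing forbids adding counts to the report. True, but the plan states a rule for each outcome, and counts for WHO class are not in it.

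**Conclusion.** The point holds as a minor reporting matter. Section 2.5.2 applies a summary for continuous data to a four-category secondary endpoint, and at n = 27 that summary gives one printed result for 49 different outcomes, among them 6 improved with none worsened and the reverse. That loss does not depend on any test or significance threshold.

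The size rests on assumed one-class shifts, 27 analysed subjects and the usual quartile definitions. How likely the trial is to fall in this range cannot be judged, because no rate of class change is given. Sample size, the primary endpoint, the PVR analysis and the stopping rules do not use WHO class and are unaffected.

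**What to change.** In Section 2.5.2, exempt WHO Functional Class from the median (IQR) rule. Report instead the number and percent improved, unchanged and worsened from baseline to Week 12, with exact 95% confidence intervals, and a baseline-by-Week-12 shift table. In the 6-0 example the report would read 6 of 27 improved, 22.2% (8.6% to 42.3%), and 0 of 27 worsened, which cannot be mistaken for its mirror. The signed-rank test can stay, stated to be in its exact form.

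The cost is one sentence and one table. No new data, visits or subjects are needed.

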**Class    Patient Symptoms**

---

I	No limitation of physical activity. Ordinary physical activity does not cause undue fatigue, palpitation, dyspnea (shortness of breath).
II	Slight limitation of physical activity. Comfortable at rest. Ordinary physical activity results in fatigue, palpitation, dyspnea (shortness of breath).

---

III	Marked limitation of physical activity. Comfortable at rest. Less than ordinary activity causes fatigue, palpitation, or dyspnea.
IV	Unable to carry on any physical activity without discomfort. Symptoms of dyspnea at rest. If any physical activity is undertaken, discomfort increases.

**Health Related Quality of Life Questionnaire:** The PAH-SYMPACT® will be utilized for measuring patient reported outcomes (PROs) for subjects with PAH. The PAH-SYMPACT® is a PRO instrument consisting of 12 symptoms and 11 impact items developed based on interviews of PAH patients and following FDA PRO guidance.

### Other Assessments

**Intravenous glucose tolerance test (IVGTT):** The IVGTT is considered a gold-standard test to measure insulin secretion and sensitivity. It has been standardized and used worldwide for more than 20 years. In our study, the expected duration is 180 mins after the test is started with an IV glucose bolus of 0.3g/kg. After the glucose bolus, a small dose of human regular insulin is given IV to moderate the plasma glucose rise. The insulin dose is 25 mUnits/Kg body weight. Patients taking oral hypoglycemics may be asked to hold those medications the morning of the IVGTT but can resume taking them following the completion of the IVGTT the same day.

**Pharmacokinetics:** Blood samples (approximately 5 mL each) will be collected during each visit as outlined below in **Table 1** to determine the concentrations of CXA-10 and two major metabolites (10-NO2-octadec-8-enoic acid [8, 9 alkene] and 10-nitro-octadecanoic acid [NO2-stearic acid]). Other metabolite concentrations may be determined as appropriate in compliance with regulatory guidance. Samples will be analyzed using a validated high performance liquid chromatography/tandem mass spectrometry (HPLC/MS/MS) assay. One aliquot will be used for identification of the distribution of CXA-10 and metabolites in lipoproteins.

**Table 1. Population PK/PD Blood Sampling Windows**

	Visit 1 (screening) (If RHC needed)	Visit 3* (Week 0)	Visit 4 (Week 4)	Visit 5 (Week 8)	Visit 7 (Week 12)	Visit 8* (Week 12)
PK/PD Sampling Window	Pre-dose	Pre-dose	Pre-dose	Pre-dose	Pre-dose	Pre-dose
PK/PD Sampling Window	2-4 hours post-dose	2-4 hours post-dose	2-4 hours post-dose	2-4 hours post-dose	4-6 hours post-dose	4-6 hours post-dose

\* Blood samples for both PK/PD studies will be collected at Visit 3 (Week 0) and Visit 8 (Week 12).

Every effort should be made to collect samples at times spread throughout the time window (i.e., avoid collections from all subjects at the same time within a window or only at the extremes of a time window; e.g. 2-4 hrs time window-not all samples at 2.5 hours). The actual time at which the subject is dosed prior to the PK sample must be recorded, and the exact time at which the PK sample is drawn must be documented in the CRF.

**Pharmacodynamics:** Coupled with PK studies, blood samples will be collected as the same times as PK samples at Weeks 0 and 12 to measure cytokines reflective of NFkB inhibition via IL-17,

IL-6, TNFa, MCP-1; Nrf2 activation via NQ01/HO-1; key PAH/metabolic syndrome biomarkers – ET-1, BMPR-1, leptin, CRP; F2a-isoprostane as an oxidative stress biomarker. A minimum 12 hour fast prior to the collection of the leptin sample will be required.

Additional biomarkers appropriate to the disease or to the pharmacology of CXA-10 may be examined in these samples depending on emerging science. It is possible that not all samples will be analyzed. Subjects' blood samples collected from baseline until the end of the study will be batched and stored at [name] lab located at the University of Pittsburgh Biomedical Science Tower (BST) until analysis.

**Microbiome:** Studies of the microbiome's impact on the development of diseases such as PAH are in early stages, and much remains unknown. To explore the associations between oral and gut bacterial and cardiovascular disease, we will obtain oral (saliva, tongue scraping) and stool samples from each subject pre and post drug treatment. Unstimulated saliva will be collected in a sterile specimen cup. Tongue scraping will be collected with a sterile scraper over the dorsum of the tongue. Stool samples will be collected using a stool collection kit. Participants will return their biospecimens in a pre-stamped envelope. Stool collection kit may be provided to subjects for home collection. Subjects may return their samples in a pre-stamped envelope by mail. Microbiome samples will be stored at [name] lab in BST until analysis.

Microbiome analyses will be performed to determine if oral and gut samples from PAH patients differ in overall bacterial community structure. We will compare functional properties of the oral and gut microbiomes in relate these findings to PAH clinical severity and outcomes using network analyses.

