#### Visit 2 (Week 0- Baseline testing)

This visit will take place at UPMC Montefiore. Subjects will be asked to fast a minimum of 12 hours to perform the assessments listed below.

- Brief physical exam with a body weight measurement and WHO Functional class assessment
- Vital signs (temperature, blood pressure, respiratory rate, heart rate, and pulse oximetry measurements are taken).
- ECG
- Echocardiogram (this test may be completed at any visit prior to first dose of drug)

- Clinical laboratory tests and urinalysis (fasting glucose, comprehensive metabolic panel, fasting lipid profile, CBC/Diff/Plt, uric acid, PT/INR)
- Research blood samples for biomarkers, cytokines measurements NT-proBNP
- Urine pregnancy test for female child-bearing potential
- IVGTT
- Health related quality of life questionnaire - Pulmonary Arterial Hypertension-Symptoms and Impact (PAH-SYMPACT®)
- Return accelerometer for data download
- Concomitant medications assessment
- AE assessment

Visit 3 (Week 0 – First dose)

This visit will take place at UPMC Montefiore. Subjects do not need to fast for this visit and this visit will last up to about 4 hours.

- 6MWT
- Blood draw for Population PK sampling (pre-dose and 2-4 hours after taking the study drug)
- Research blood samples for biomarkers, cytokines measurements (samples collected at the same times as PK samples)
- Subjects will be instructed to take the first dose of study medication at the clinic after a breakfast/morning snack containing up to approximately 30% fat
- Dispense study drugs
- Concomitant medications assessment
- AE assessment

Visit 3a (Week 1: +3d)

This visit will take place at UPMC Montefiore or UPMC Presbyterian. This visit will last approximately 30 minutes. Subjects who are on warfarin will be asked to return to the clinic one week after taking the study drug for a blood draw for PT/INR. If the INR value is > 2.5, the warfarin dose may be adjusted per the standard of care. Subjects do not need to fast for this visit.

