**Visit 8 (Week 12 – End of treatment)**

This visit will take place at UPMC Montefiore and the visit will last up to about 7 hours. The subject does not need to fast.

- 6MWT
- Blood draw for Population PK sampling (pre-dose and 4-6 hours after taking the study drug) Subjects will be instructed to take the study medication at the clinic after a breakfast/morning snack containing up to approximately 30% fat
- Research blood samples for biomarkers, cytokines measurements (samples collected at the same times as PK samples)
- Concomitant medications assessment
- AE assessment
- Dispense 1st month of open label CXA-10 after the completion of all end of treatment testing (optional)

Following the completion of all end of treatment assessments, patients have the option to discontinue treatment and have a safety follow up at Visit 9 or patients may also choose to enter the open label extension for 6 months. If patients are in the open label extension, Visit 9 will be the month 1 follow up. If patients wish to enter the open label extension, the first month supply will be dispensed at the end of their final visit for end of treatment testing.

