### **2.2.3 Description of Study Procedures**

Subjects must present to all study visits in the morning. Subjects must fast from all food and drink (except water) for a minimum of 12 hours prior to Visits 2 and 6 (12-hour fast is required for leptin analysis). Subjects must fast from all food and drink (except water) for a minimum of 8 hours prior to visits 1, 4, 5, 7, 9.

During treatment visits (Visits 3 through 9), when at the study site, subjects will have access to breakfast, lunch and dinner if appropriate. Subjects will eat breakfast or a morning snack (containing no more than 30% fat) after completion of all pre-dose assessments and just prior to

the time of dosing. Subjects will be instructed to take their dose of study medication at the clinic at each scheduled office visit (Visits 3, 4, 5, 7, 8). The date and time of dosing will be recorded at these visits.

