## 2.5.4 Pharmacodynamics Analyses

### 2.5.4.1 Biomarker Analyses

PD endpoints will be listed and summarized descriptively by assessment time. Change from baseline in lipid profile (e.g. total cholesterol and triglycerides) will be separately analyzed using an appropriate model. Additional biomarkers (e.g. leptin, MCP-1, IL-6, etc.) may also be analyzed as appropriate. Relevant covariates (e.g. underlying disease) will be included. The

least square mean difference and associated 95% confidence intervals for each assessment time and across all assessment times will be obtained from the model.

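### Leptin is tied to the PK-coupled samples at Visits 3 and 8, where the protocol's own 12-hour fast does not apply; the fasted samples at Visits 2 and 6 should be named as its source

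*Combined protocol and SAP*

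**What the plan says.** Section 2.2.3 (Pharmacodynamics) describes the panel this way: "Coupled with PK studies, blood samples will be collected as the same times as PK samples at Weeks 0 and 12". Leptin is on the list that follows: "BMPR-1, leptin, CRP; F2a-isoprostane as an oxidative stress biomarker". The paragraph ends with the fasting rule: "A minimum 12 hour fast prior to the collection of the leptin sample will be required". The footnote to Table 1 assigns the joint sampling to particular visits: "Blood samples for both PK/PD studies will be collected at Visit 3 (Week 0) and Visit 8 (Week 12".

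The visit descriptions in Section 2.2.2 say otherwise about fasting. For Visit 3: "Subjects do not need to fast for this visit and this visit will last up to about 4 hours". For Visit 8: "The subject does not need to fast".

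The opening of Section 2.2.3 places the 12-hour fast at Visits 2 and 6 and gives the reason: "12-hour fast is required for leptin analysis". Visits 1, 4, 5, 7 and 9 carry an 8-hour fast. The same section has subjects eat once the pre-dose assessments are finished and immediately before the clinic dose.

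Section 2.5.4.1 says that leptin may be modelled, and that the model will give the "least square mean difference and associated 95% confidence intervals for each assessment time and across all assessment times". It does not restrict samples by feeding state.

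**The concern.** Site staff cannot follow all of these instructions together. If leptin is drawn with PK at Visits 3 and 8, the fasting rule is not met. If it is drawn at the fasted visits, the coupling to PK is not met.

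Two analyses are exposed. The first is the exploratory PK/PD relationship for leptin, which needs a leptin value and an exposure value that belong together. The second is any leptin model under Section 2.5.4.1 that takes in the Visit 3 and 8 samples, because feeding state would then vary between samples within the estimate.

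Leptin also has a place in the rationale. Section 1.3.5 uses it as human evidence of a metabolic effect, quoting a mean difference of -2640 (95% CI -6170 to 890). The half-width of that interval is (890 + 6170) / 2 = 3530, larger than the estimate itself. A marker this imprecise is poorly placed to absorb an avoidable source of variation.

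**Working it through.** The plan gives no figure to reproduce here, so the check sets visits against conditions.

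**Step 1: visits by fast, PK draw and research blood** (Sections 2.2.2 and 2.2.3, Table 1, Appendix A)

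| Visit | Required fast | PK draw | Research blood |
|---|---|---|---|
| 1 | 8 h | yes, if RHC needed | yes |
| 2 | 12 h | no | yes |
| 3 | none | pre-dose, 2-4 h post-dose | yes |
| 4 | 8 h | pre-dose, 2-4 h post-dose | yes |
| 5 | 8 h | pre-dose, 2-4 h post-dose | yes |
| 6 | 12 h | no | yes |
| 7 | 8 h | pre-dose, 4-6 h post-dose | yes |
| 8 | none | pre-dose, 4-6 h post-dose | yes |
| 9 | 8 h | no | yes |

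Visits with a 12-hour fast: 2 and 6. Visits with PK: 1, 3, 4, 5, 7 and 8. The two sets do not overlap, so 0 of 9 visits meet both conditions.

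**Step 2: the draws at the two named visits.** Visits 3 and 8 each have a pre-dose and a post-dose draw, which makes 2 × 2 = 4 leptin draws per subject if Section 2.2.3 is followed literally.

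- Two pre-dose draws: no fast is required. Some subjects may happen to have fasted, but I found no instruction to record it.
- Two post-dose draws: the meal comes just before the dose, so time since food is about 2-4 h at Visit 3 and 4-6 h at Visit 8. Against 12 h, the shortfall is at least about 12 - 4 = 8 h at Visit 3 and 12 - 6 = 6 h at Visit 8. These draws cannot comply, and would not comply even if an overnight fast were added.

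So none of the 4 draws is assured to meet the rule, and 2 of the 4 cannot. Visit 7 is also a Week 12 PK visit, but its 8-hour fast is 4 h short of the minimum.

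**Step 3: effect on a leptin estimate.** The post-dose windows differ between Week 0 (2-4 h at Visit 3) and Week 12 (4-6 h at Visit 8). Even a post-dose to post-dose comparison would therefore change time since food along with time on treatment. An average over all times would add 12-hour-fasted and unfasted samples to that. The documents give no figure for the effect of a meal on leptin, so the size of any distortion cannot be calculated from them.

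**Step 4: what remains usable.** Visits 2 and 6 both have research biomarker blood and the 12-hour fast. That is a complete fasted pair for change from baseline at 12 weeks.

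**The case against.** The strongest reply is that the protocol already handles leptin. Section 2.2.3 ties the 12-hour fast at Visits 2 and 6 to leptin by name, and both visits draw research blood. A careful reader would take leptin from there and regard the Table 1 footnote as applying to the other markers. This stands as far as the change-from-baseline endpoint goes. It does not remove the conflict, because leptin is listed by name in the PK-coupled panel.

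A reader might infer more than the documents support, in four ways.

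- *That the leptin endpoint is invalid.* It is not. The fasting failure concerns leptin drawn at Visits 3 and 8 only.
- *That leptin PK/PD is impossible without a same-visit sample.* Section 2.5.3 plans population PK, which can predict exposure at Visit 6. Subjects record their dose times, the home dose is withheld before Visits 6, 7 and 8 (Section 2.3.2), and Section 2.2.2 puts steady state by day 7. Pre-dose PK at Visits 7 and 8 is therefore informative about Visit 6. One limit remains: the three end-of-treatment visits need not run in sequence, and Visits 7 and 8 have no stated day window, so the interval will vary.
- *That Section 2.5.4.1 commits to pooling fed and fasted leptin.* It commits to a model for lipids and leaves leptin optional, with per-time estimates as well as an overall one. Pooling is permitted, not prescribed.
- *That every research-blood draw is a leptin draw.* Section 2.2.3 places the pharmacodynamic panel at Weeks 0 and 12 and allows that some samples will not be assayed. A tally of all research tubes would overstate the problem.

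**Conclusion.** The contradiction is real and of minor severity. No visit satisfies both the 12-hour fast and the coupling to PK, so leptin taken with PK at Visits 3 and 8 fails the protocol's own condition. The damage is confined to the leptin PK/PD analysis and to any leptin estimate that includes unfasted or post-meal samples. Leptin and PK/PD are exploratory, and the PK/PD work is conditional on the data. Safety, PVR and sample size are not touched.

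This rests on three assumptions: the fasting rule is meant to apply to every leptin sample, as its wording says; site staff follow the stated fasts and no more; and Visit 2 serves as the leptin baseline. On the last, the study design overview has the first 10 subjects dosed at the screening catheterization, so for up to 10 subjects Visit 2 may follow one dose of study drug. The report should identify them.

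**What to change.** 1. In Section 2.2.3 (Pharmacodynamics) and the Table 1 footnote, state that leptin is measured in the 12-hour-fasted research samples at Visits 2 and 6, and remove it from the PK-coupled panel at Visits 3 and 8.
2. In Section 2.5.4.1, restrict any leptin model to those fasted samples, with Visit 2 to Visit 6 as the change from baseline.
3. For leptin PK/PD, link Visit 6 leptin to exposure predicted by the population PK model in Section 2.5.3, or to the pre-dose PK at Visits 7 and 8, and report the interval between the samples.
4. Record fasting status at each research-blood draw.

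The cost is protocol wording and one case report form item. There will be no simultaneous leptin-PK pair and no post-dose leptin, a loss limited to an exploratory analysis. The change should be made before the stored samples are assayed.

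I would not add a 12-hour fast at Visits 3 and 8. It would leave the post-dose draws non-compliant and add two long fasts. Moving the six-minute walk after the snack to accommodate it would disturb the Week 0 assessment of a secondary endpoint for the sake of an exploratory marker.
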